**6) Study Timelines\***

- a. Subject participation will be approximately 11 days from the time of consent to the last blood draw. After the last blood draw, only routine clinical data will be followed and captured from the medical record to outcomes.
- b. Enrollment of 75 subject will be over the course of 12 to 18 months.
- c. The primary analyses should be completed within 24 months from the time of study initiation.

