**7) Study Endpoints\***

The Primary endpoint is change from baseline in the ISTH DIC Score to Day 9.

The Secondary endpoints include change from baseline D-dimers, Fibrinogen & Prothrombin time, length of hospital stay (days), mortality (%), and Pulmonary function (including Time (days) to mechanical ventilation and/or ECMO Duration (days) of new ventilator or extracorporeal membrane oxygenation (ECMO) use, Change from baseline SOFA and SOFA Respiratory sub-score, Number of venous thromboembolisms, Number of major bleeding events

Subjects discharged prior to completion of intervention would be classified as having a successful outcome. We anticipate that all cause morbidity will occur in 10-20% of the COVID study population, despite standard of care. We anticipate that these patients will be deficient in endogenous AT3.

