### **Procedures for Reporting Adverse Events**

Adverse events may be spontaneously reported, obtained through non-leading questioning, or noted during examination of a subject. Adverse events will be recorded from the signing of informed consent through the last dose of study drug. Serious adverse events will be recorded from the signing of informed consent through hospital discharge.

At each visit, new AEs are recorded sequentially on the **Adverse Event log**. The AE term will note the diagnosis whenever possible, not the individual signs or symptoms (e.g., myocardial infarction will be recorded rather than chest pain, elevated cardiac enzymes, and abnormal ECT). Also recorded are:

- Start and stop date and time
- Whether or not the event is continuing
- Severity (mild, moderate, severe)
  - Mild: usually transient, requiring no special treatment and generally not interfering with usual daily activities
  - Moderate: usually ameliorated by simple therapeutic maneuvers and impairs usual activities
  - Severe: requires vigorous therapeutic intervention and interrupts usual activities. Hospitalization may or may not be required.

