**DRUG INTERACTIONS**

The anticoagulant effect of heparin is enhanced by concurrent treatment with THROMBATE III in patients with hereditary AT deficiency. Thus, in order to avoid bleeding, the dosage of heparin (or low molecular weight heparin) may need to be reduced during treatment with THROMBATE III.

The effect of drugs that use antithrombin to exert their anticoagulation may be altered when THROMBATE III is added or withdrawn. We will regularly perform coagulation tests suitable for the anticoagulant used (e.g., aPTT and anti-Factor Xa activity) and at close intervals to avoid excessive or insufficient anticoagulation. Adjust dosage of anticoagulant as necessary. Additionally, we will monitor the patients for the occurrence of bleeding or thrombosis.

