**Appendix B**

Study Subject Flowsheet	Enrollment - Day 1*	Days 3, 5, 7 & 9	Day 11	On Discharge
Informed Consent	x			
Entry Criteria	x			
Demographics	x			
Medical and Surgical History	x			
Prior & Concomitant Medications	x	x	x	x
Vital Sign Measurements	x	x	x	
ISTH DIC Score	x	x	x	
SOFA Score	x		x	
Blood Draw	x	x	x	
Urine or Serum Pregnancy Test if applicable	x			
Platelet	x	x	x	
PT, INR	x	x	x	
PTT	x	x	x	
Hemoglobin and Hematocrit	x	x	x	
Fibrinogen	x	x	x	
D-Dimer	x	x	x	
AT3 Level	x	x	x	
Anti-Xa	x	x	x	
Dosing if randomized to group with AT3 Infusion 	x 	x 		
Adverse Events 	x	x	x	x 
Hospital LOS				x
Mortality				x
PF ratio change				x
Days on Ventilator				x
Days on ECMO				x
VTE's				x
Bleeding Events				x

\*: Day refers to a 24 hour period.

x: To be completed

1: Only if randomized to AT3 Infusion and AT3 level is at specified level

2: Only Serious Adverse Events will be captured from last dose to hospital discharge.

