### Appendix C

The Secondary endpoint measurements:

- a. D-dimer level change from baseline to Day 9 in mcg/mL FEU or DDU,
- b. Fibrinogen level change from baseline to Day 9 in mg/dL
- c. Prothrombin time change from baseline to Day 9 in seconds
- d. Length of hospital stay in days,
- e. Mortality (%) of overall and between groups,
- f. Pulmonary function
  - a. Time (days) to mechanical ventilation and/or
  - b. ECMO Duration (days) or extracorporeal membrane oxygenation (ECMO) use,
- g. SOFA score change from baseline to Day 9 and
- h. SOFA Respiratory sub-score change from baseline to Day 9,
- i. Number of venous thromboembolisms from admission to hospital discharge,
- j. Number of major bleeding events from admission to hospital discharge

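### Serious events, VTE and major bleeding are collected only to hospital discharge, leaving early-discharged treated patients with little post-infusion safety data and any by-arm reading of the counts dependent on length of stay

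*Combined protocol and SAP*

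**What the plan says.** Three collection windows end at discharge.

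- **Serious adverse events.** Section 10, under the reporting procedures, says: "Serious adverse events will be recorded from the signing of informed consent through hospital discharge". The Serious Adverse Events paragraph of the same section sets the same end, as does footnote 2 of the Appendix B flowsheet: "Only Serious Adverse Events will be captured from last dose to hospital discharge".
- **VTE.** Appendix C, item i: "Number of venous thromboembolisms from admission to hospital discharge".
- **Major bleeding.** Appendix C, item j: "Number of major bleeding events from admission to hospital discharge". In Appendix B, VTE and bleeding are marked only in the discharge column, which is the last one.

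Non-serious events stop sooner: "Adverse events will be recorded from the signing of informed consent through the last dose of study drug".

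Four other places bear on this. Section 6 says "Subject participation will be approximately 11 days from the time of consent to the last blood draw" and adds that routine record data are then followed to outcomes, with no end date. Section 7 says "Subjects discharged prior to completion of intervention would be classified as having a successful outcome". Section 8 schedules infusions on Days 1, 3, 5, 7 and 9, each conditional on an AT3 level below 100%. Section 12 makes any major bleeding event a reason to pause the study. No post-discharge call, visit or record check is described.

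**The concern.** There are two problems.

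The first is missing safety data. The patients whose observation ends soonest after an infusion are treated patients who go home early, and the plan expects some of these. An event after they leave falls outside every stated window. The Section 12 pause depends on major bleeds becoming known to the study.

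The second is interpretation. VTE and major bleeding are listed secondary endpoints expressed as plain numbers. In a trial that randomizes 25 against 25, a reader will set those numbers side by side. The time over which each patient can contribute an event depends on length of stay, which is itself a secondary endpoint, and on survival. A group that leaves hospital or dies sooner can show fewer events at the same underlying risk. The count also starts at admission, whereas Day 1 is enrollment, so events that preceded randomization can be included.

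**Working it through.** The plan states no event rate, event count or power calculation for safety, so there is no figure of its own to reproduce.

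**Step 1: follow-up from the dosing calendar (Sections 6 and 8).** Take infusions on Days 1 and 3 and discharge on Day 4.

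- Observation after the last infusion: 4 − 3 = 1 day.
- Participation days not observed: 11 − 4 = 7 of about 11.
- More generally, a patient discharged after the Day 3 infusion and before the Day 5 one has less than 5 − 3 = 2 days after the last infusion and less than 5 − 1 = 4 days after the first.

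Such a patient is under-observed because of discharge. Few infusions alone do not imply it, since a dose is also omitted when AT3 is not below 100%, and that patient may remain in hospital under observation.

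**Step 2: effect of unequal stay on the counts.** Inputs: 25 patients per arm (Section 4). Assumptions, not in the documents: an event hazard of 1% per day, equal in both arms, and every patient in an arm staying the same number of days d. Then the proportion with an event is 1 − 0.99^d, and the expected number is 25 times that.

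| Stay (days) | Proportion with event | Expected per 25 | Ratio | Spurious reduction |
|---|---|---|---|---|
| 12 vs 12 | 11.4% vs 11.4% | 2.8 vs 2.8 | 1.00 | 0% |
| 12 vs 11 | 11.4% vs 10.5% | 2.8 vs 2.6 | 0.92 | 8% |
| 12 vs 9 | 11.4% vs 8.6% | 2.8 vs 2.2 | 0.76 | 24% |
| 14 vs 10 | 13.1% vs 9.6% | 3.3 vs 2.4 | 0.73 | 27% |

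At a low hazard the ratio is close to the ratio of stays: 11/12 = 0.92, 9/12 = 0.75, 10/14 = 0.71. The percentages therefore mostly restate the assumed difference in stay. The choice of hazard matters little: for 8 versus 10 days, an assumed risk of 5% per 10 days gives a ratio of 0.80, and 15% per 10 days gives 0.81. With one fixed window and equal hazards the ratio is 1.00.

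**Step 3: is there an analysis that would correct for this?** Section 9 compares the fastest with the slowest recoverers. It contains no person-time, fixed-window or competing-event method. In Appendix C only mortality is described as being reported between groups.

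**The case against.** Several points on the other side have force.

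- **No comparison is planned.** A reader might infer that the trial will test VTE and bleeding between arms over unequal time. The documents do not support that. Section 9 has no such test, and items i and j of Appendix C are plain counts in a pilot. This stands. What remains is the by-arm reading that listed endpoints invite, and the lost safety data, which matter with or without a test.
- **Record follow-up may go further.** Section 6 captures record data to outcomes, Section 8 says all subjects are followed for endpoints and adverse events, and Appendix B marks adverse events at Day 11. None of these says that collection continues after discharge, while Section 10, Appendix B footnote 2 and Appendix C name discharge as the end. The result is an ambiguity to be reconciled.
- **The drug-interaction warning.** Section 13 says: "The effect of drugs that use antithrombin to exert their anticoagulation may be altered when THROMBATE III is added or withdrawn". A reader might infer that discharge cuts off exactly this withdrawal period. That would require early-discharged patients to be taking such drugs at home, which the documents do not say. The same section also provides for coagulation tests and for monitoring of bleeding and thrombosis. The point does not rest on this sentence.
- **The bias is assumed.** A reader might take 24% or 27% as the expected distortion. The documents give no distribution of stay and no post-discharge event rate. A constant hazard also ignores that a VTE or major bleed can itself prolong the stay. This stands, and is why the range must include zero.

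**Conclusion.** The concern holds as a gap in safety collection and a limit on interpretation. Serious events, VTE and major bleeding are not collected after discharge, early discharge is foreseen, and a patient leaving on Day 4 after two infusions has about one day of post-infusion observation. These facts come from the text and the dosing calendar and need no assumption.

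The effect on by-arm counts is real in principle but of unknown size. Under the stated assumptions it runs from nothing to about 27%. The largest scenario shown is a difference of 3.3 − 2.4 = 0.9 expected events per 25 patients. That is small in absolute terms, although with so few events expected, one or two missed could alter the safety picture. The primary endpoint, the change in ISTH DIC score to Day 9, is outside this point. It is a worthwhile and inexpensive improvement.

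**What to change.** Amend Section 10 (reporting procedures and the Serious Adverse Events paragraph), Appendix B and Appendix C as follows.

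1. Collect serious adverse events, VTE and major bleeding in all three groups through Day 11 or discharge, whichever is later. For patients already home, use one Day 11 call or record check. Day 11 is the protocol's existing horizon.
2. As the main by-arm summary, count VTE and major bleeding from randomization to Day 11, and from enrollment to Day 11 in the group with AT3 at or above 100%. Moving only the end of the window would not be enough, because a count from admission still has unequal length and admits events before randomization.
3. Report deaths before Day 11 alongside as a competing event, and state how many patients withdrew before Day 11.
4. Keep the counts to discharge as supportive, expressed per patient-day in hospital, using the length of stay already collected.
5. State in Section 6 when record follow-up ends, so that it agrees with Section 10 and Appendices B and C.

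The cost is one contact or record check for each patient discharged before Day 11, and minor changes to consent and IRB wording. No visit or blood draw is added. Ascertainment after discharge will be somewhat less complete than in hospital, so the report should say how many patients in each group had their Day 11 status obtained that way.

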### **Relationship to Study Medication**

The relationship of an AE to the administration of study medication (unrelated, probable or definite) is a clinical decision based on all available information at the time of review. The relationship will be evaluated according to the following definitions:

**Unrelated:** includes the existence of a clear alternative explanation (e.g., mechanical bleeding at surgical site) or non-plausibility (e.g., the patient is struck by an automobile, at least where there is no indication that the study medication caused disorientation that may have led to the event; cancer developing a few days after study medication administration).

**Probable:** The AE, including clinical laboratory abnormality, follows a reasonable sequence from the time of study medication administration, follows a known response pattern of the study medication class, is unlikely to be attributed to the patient's clinical state, and is confirmed by improvement on stopping the study medication (de-challenge).

**Definite:** The AE, including clinical laboratory abnormality, follows a plausible sequence from the time of study medication administration; follows a known or expected response pattern to the study medication class; cannot be explained by disease or it disappears or decreases on cessation or reduction in study medication dose; and/or it reappears or worsens when the study medication is re-administered.

**Actions taken** (none, study drug dose interrupted, study drug discontinued, change in treatment).

**Outcome** (resolved, severity or frequency increased, ongoing, fatal). An individual AE receives only one outcome.

Adverse events not resolved at the end of treatment will be followed until discharge or until the AE is judged by the investigator to have stabilized.

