### **List of Expected Adverse Events**

Acute respiratory failure; respiratory distress; acute lung injury; acute respiratory distress syndrome (ARDS); acute renal failure; coagulation dysfunction; decreased platelets count; neutropenia; hypothermia; fever, bacteremia; sepsis, septic shock; hypotension; metabolic acidosis, pleural effusion; abdominal compartment syndrome; repeated surgeries/debridement; amputation.

For purposes of this study, deaths will be captured as clinical outcomes and do not need to be reported as SAEs unless felt related to study drug administration.

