### **11) Withdrawal of Subjects\***

The occurrence of any of the following events may necessitate premature withdrawal of a subject from the study:

- Development of any of the following Inclusion/Exclusion criteria:
  - Subjects with a "do not resuscitate" order,
  - Multi-organ failure,
  - History of hypersensitivity or allergy to any component of the study drug,
  - Ongoing massive surgical or unexplained bleeding,
  - History of bleeding or clotting disorder,
- Occurrence of a serious adverse event (SAE) thought to be related to study drug and not alleviated by symptomatic treatment
- Unwillingness to continue in the clinical study
- Death of the subject
- Principal Investigator decision (i.e. subject non-compliance with study procedures)
- Significant AE or medical decision that precludes the subject from adhering to study requirements

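### The causality scale cannot rate a fatal or post-last-dose event as probable and has no level for uncertain cases, so a possibly drug-related death may go unreported as an SAE

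*Combined protocol and SAP*

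**What the plan says.** Under *Relationship to Study Medication* (Section 10), the permitted ratings are "unrelated, probable or definite". *Unrelated* is described by a clear alternative explanation or by non-plausibility. *Probable* asks for a reasonable time sequence, a known response pattern and a low likelihood that the patient's own condition is the cause, and then adds that the event "is confirmed by improvement on stopping the study medication (de-challenge". *Definite* asks for a plausible sequence and a known or expected pattern, and that the event "cannot be explained by disease or it disappears or decreases on cessation or reduction in study medication dose", and/or that it returns or worsens on re-administration. The AE outcomes listed there are "resolved, severity or frequency increased, ongoing, fatal). An individual AE receives only one outcome".

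Under *List of Expected Adverse Events* (Section 10), "deaths will be captured as clinical outcomes and do not need to be reported as SAEs unless felt related to study drug administration".

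Three other places bear on the point. *Serious Adverse Events* (Section 10) sends every serious event, from consent to discharge, to the SAE log without a causality condition. *Stopping rules* (Section 12) pauses the study and triggers an FDA report for any major bleed, any anaphylaxis or two infusion reactions, also without a causality condition; death is not listed. Mortality is a secondary endpoint (Section 7, Appendix C).

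**The concern.** The rating that an investigator would naturally use for a suspected drug reaction depends on an observation that a death cannot supply. The scale also has no level for the commonest hard case in this population, an event that either the drug or the disease could have caused. Section 2 describes these patients as prone to both clotting and bleeding, and the expected-event list covers respiratory failure, coagulation dysfunction, sepsis and shock. A disease explanation will therefore often be available.

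Relatedness then decides whether a death is reported as an SAE. If the scale gives no usable answer and the exemption does not define its own test, two investigators could handle the same death differently. A safety signal in a 25-patient arm could then surface only as a mortality count, without case review for causality.

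**Working it through.** No figure in the plan is at issue, so the check is mainly a reading of the definitions against each other.

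**Step 1. Logic of each level.** The conditions for *probable* are joined by *and*, so improvement on stopping is required. For *definite* it is one alternative among several. *Unrelated* needs a clear alternative or non-plausibility; uncertainty alone does not meet it.

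**Step 2. Apply the levels.**

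| Event | Unrelated | Probable | Definite |
|---|---|---|---|
| Reversible, during dosing, unlikely to be disease | No | Yes, if it improves on stopping | Possible |
| Fatal | Only with a clear alternative or non-plausibility | Never: an AE has one outcome, and a fatal one has not improved | Only if disease cannot explain it, or by recurrence on re-administration |
| Serious, starting after the last dose | Same | Never: no dosing is left to stop | Only if disease cannot explain it |
| Plausibly drug or disease, no informative de-challenge | No: alternative not clear, drug not implausible | No | No |

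Two defects follow. The last row has no valid rating. The scale is also out of order, because a death can reach *definite* but not *probable*. The third row matters because SAEs are collected until discharge, after dosing has ended (*Procedures for Reporting Adverse Events*; Appendix B, note 2).

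**Step 3. Follow a death to reporting.** A fatal major bleed or fatal anaphylaxis reaches Section 12 whatever its rating. Any other death, such as one from thrombosis or respiratory failure, reaches SAE reporting under the exemption only if it is felt related. The text does not say whether that means *probable* or *definite*, or any suspicion at all. *Serious Adverse Events* logs all serious events while the exemption excuses deaths, and the two are not reconciled.

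**Step 4. How often the exemption would come into play.** Inputs: 25 AT3 patients (Section 4); mortality of 11.5% in a cited series of 183, and 10% (ICU) and 12.5% (hospital) in a cited series of 40 (Section 2). It is an assumption that these rates apply here. Expected deaths = n × p; chance of at least one = 1 − (1 − p)^n.

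- p = 0.10: 25 × 0.10 = 2.5; 1 − 0.90^25 = 0.93
- p = 0.115: 25 × 0.115 = 2.9; 1 − 0.885^25 = 0.95
- p = 0.125: 25 × 0.125 = 3.1; 1 − 0.875^25 = 0.96

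Section 3 excludes patients expected to die within 24 hours, those with a do-not-resuscitate order and those with multi-organ failure, so the true rate may be lower. Halving the lowest rate to 5% gives 25 × 0.05 = 1.25 deaths and 1 − 0.95^25 = 0.72.

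**The case against.** The best defence is that the plan leaves causality to judgement: "The relationship of an AE to the administration of study medication (unrelated, probable or definite) is a clinical decision based on all available information". The exemption says 'felt related' and cites no rating, so an investigator who suspects the drug may report a death without meeting the de-challenge condition. *Definite* does not require de-challenge. The harm most expected from AT3 given with heparin is bleeding (*Drug Interactions*, Section 13), and major bleeding is caught by Section 12 regardless of cause. Serious events go to the log, fatal is a recognised AE outcome, and mortality, venous thromboembolism and major bleeding are all endpoints.

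All of this stands, and it limits the point to SAE reporting of deaths outside the Section 12 triggers. It does not repair the scale. The definitions are given as the basis for rating, yet they cannot be met by the events just described, and freedom to report on judgement is not a rule that investigators will apply alike.

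A reader might infer that unclassifiable events default to *unrelated*. No default is written, and an uncertain event does not meet that definition either. A reader might also infer that the withdrawal rule is weakened. Section 11 turns on "Occurrence of a serious adverse event (SAE) thought to be related to study drug", which is again not a scale level, is only one of several grounds, and concerns living patients, so the problem with fatal events does not carry over.

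**Conclusion.** The concern holds as a defect in the safety-reporting wording. Read as written, no fatal or post-last-dose event can be rated *probable*, and an event plausibly due to either cause has no rating. The death exemption depends on a relatedness judgement that is not tied to the scale. A possibly drug-related death without major bleeding or anaphylaxis may therefore go unreported as an SAE, while still being counted in mortality.

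It would be too strong to say that a death cannot be called related, or that the roughly three expected deaths would all escape SAE review. The 2.5 to 3.1 figure is background mortality under an assumed rate. Many such deaths may be plainly due to disease, which is what the exemption is meant for. The figure shows only that the exemption will probably be used in the AT3 arm; the documents give no basis for estimating how many deaths would be misrated.

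**What to change.** In *Relationship to Study Medication*:

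- Add a level between *unrelated* and *probable* for events that either the drug or the disease could plausibly explain.
- Apply the de-challenge condition only where it can be observed, and state that it does not apply to fatal or irreversible events or to events starting after the last dose.

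In *List of Expected Adverse Events*:

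- State which ratings count as 'felt related'. Whether the new level counts is for the sponsor to decide, but it must be written down.
- Reconcile the exemption with *Serious Adverse Events*, making clear whether it covers only the death as an outcome or also the serious event that led to it.
- Require a documented causality rating for every death in the AT3 arm.

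The cost is a protocol wording change, an update to the AE log, and a few more SAE reports. Dosing, sample size and endpoints are unaffected.
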